Patients admitted with loose stools/diarrhea must be diagnosed quickly so that relevant treatment can be initiated. The current workflow of collecting stool samples from the pelvis without adding urine can extend the time to diagnosis and thus the hospitalization process, with the consequence that the patient will receive relevant treatment later.

Hypothesis

With a collection tube that can be easily inserted into the rectum, the time to collect the first usable stool sample will be shortened.

Purpose

Testing of collection tubes for stool samples.

Design

Proof of concept study, where the collection tube is tested on 50 hospitalized patients on Oncology Ward O81.

Inclusion criteria

- The patient must be at least 18 years old.
- The patient must be able to understand Danish
- All patients admitted to the Oncology ward O81 with loose stools/diarrhea. This is regardless of whether the patient is undergoing active medical cancer treatment and/or antibiotic treatment.
- It is a requirement that the patient is cognitively well-functioning and can understand the patient information related to the study.
- The patient must be able to cooperate optimally with the sampling itself. If this is not assessed at the time of admission, the patient will be excluded from the study.

Exclusion criteria

- Expected remaining life < 2 weeks

Recruitment

All patients admitted with loose stools/diarrhea will be offered the opportunity to participate in the study. They will be selected if they meet the inclusion criteria described above.

Procedures

Patients admitted with loose stools/diarrhea will have a stool sample taken with the collection tube at the time of admission.

The patient is placed on their side in a bed or on a stretcher before the actual sample collection.

The stool sample is then sent to the Microbiology Department for standard testing for Clostridium Difficile, pathogenic intestinal bacteria and viruses. No other analyses are performed and only the actual collection of the stool sample is included in the project. The stool sample taken with the collection tube replaces the stool sample with the standard method.

Method

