Age, gender, cancer diagnosis, temperature (> 38.5), neutrophil count ($< 0.5 \times 10^9 /l$), number of bowel movements in the last 24 hours, possible constipation in the last 24 hours, date of last series and type of medical cancer treatment (if applicable), date of hospitalization, date of stool sample and results of stool sample.

The above patient record information must be used to ensure that these are relevant patients in terms of being hospitalized with infectious diarrhea, as well as to describe demographics and any comorbidity.

The information that will be used in the project before consent is given from the subjects is passed on to the researcher.

The experiment has been registered with Region Zealand and is subject to the Data Protection Act and the General Data Protection Regulation .

Economy

The study is supported by the Department of Clinical Oncology and the Innovation and Technology Council at Zealand University Hospital with Match Point funding of DKK 100,000.

MatchPoint is a project under Zealand University Hospital, where innovation projects, after a professional assessment, are financially supported with DKK 100,000 for development and testing.

MatchPoint funds: DKK 100,000.

The above has financed the development of collection tubes, patent search and salaries.

Funding: the experimental group has received an Inno Explorer grant, funding the study.

There are no affiliations with any companies with an interest in the trial, among any of the participants in the trial group. The study is part of a product development, and there is no product on the market at present. A number of prototypes will be manufactured, paid for by the trial group, with funds from MatchPoint allocated to the group.

The research group has no financial interest in the study, but wishes to patent the invention.

Recruitment of subjects and informed consent

The subjects are recruited at the time of admission when the doctor records the admission record and prescribes that stool samples be taken for culture and resistance testing. The patient will be isolated and will thus be alone in a patient room, so that oral information and conversation about the study and its rationale can take place undisturbed. Written patient information will be provided.

The right to an assistant will be offered when a potential candidate for the study is identified.

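### Does the check that patients are relevant as infectious-diarrhea cases let the tube's own stool result decide who counts?

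*Protocol*

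**What the plan says.** The list of patient data in the Data storage section of the protocol ends with "date of hospitalization, date of stool sample and results of stool sample". The next sentence gives the list two purposes. The first is "The above patient record information must be used to ensure that these are relevant patients in terms of being hospitalized with infectious diarrhea". The second is "as well as to describe demographics and any comorbidity".

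Entry is governed elsewhere. The Inclusion criteria admit "All patients admitted to the Oncology ward O81 with loose stools/diarrhea", whatever their cancer or antibiotic treatment, and name no infectious cause. Under Recruitment the selection rule is "They will be selected if they meet the inclusion criteria described above". On timing, the section on recruitment of subjects and informed consent says "The subjects are recruited at the time of admission when the doctor records the admission record and prescribes that stool samples be taken".

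Under Procedures, "The stool sample taken with the collection tube replaces the stool sample with the standard method", and "only the actual collection of the stool sample is included in the project". The section on statistical considerations reduces the outcome to successful or unsuccessful in 50 patients and states that no calculation was made.

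**The concern.** Two features of the Data storage sentence look wrong.

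The first is circularity. The sentence refers back to the whole list, and the list includes the stool result. Because the tube sample replaces the standard one, that result comes from the device being tested. A tube that collects nothing usable may give no result, and such a patient could not be confirmed as infectious from it. If relevance were settled with the result in hand, membership of the study population would depend on the outcome.

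The second is the population. Hospitalized with infectious diarrhea is narrower than loose stools or diarrhea of any cause, and the Summary itself says that the diarrhea may be chemotherapy-induced.

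With a single group and a yes/no outcome, the denominator determines the reported proportion. The section on publication says the results will feed a larger study, so an inflated success rate could be carried forward.

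**Working it through.** There is no figure in the plan to reproduce: 50 was chosen by judgement, and no success rate or positivity rate is given. The check is mainly one of reading the sections together.

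**Step 1: does the sentence select anyone?** It stands under Data storage and states what the record data are for. It does not say what happens to a patient judged not relevant, and it defines no exclusion and no analysis set. The one stated selection rule is under Recruitment and points to the inclusion criteria.

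**Step 2: could the stool result enter selection?** Recruitment happens at admission, when the stool test is prescribed, and Procedures place the tube sample at admission too. The order is prescription, consent, tube, laboratory result. The result cannot inform a decision taken before it exists.

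**Step 3: must every listed item serve the relevance purpose?** No. Age and gender cannot show that diarrhea is infectious; they serve the descriptive purpose in the same sentence. The stool result can be placed there in the same way.

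**Step 4: do the two populations conflict?** Recruitment is tied to a prescribed stool test, and the Summary describes the medical-department patients as there mainly to have infection ruled out. Infectious in the sense of suspected infection fits both. Because the project covers the collection only, a pathogen-negative sample is not a failed collection.

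**Step 5: size, if a removal step were invented.** All rates here are assumptions. Exact (Clopper-Pearson) 95% limits for x successes in n are:

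- lower = Beta quantile(0.025; x, n − x + 1)
- upper = Beta quantile(0.975; x + 1, n − x)
- when x = n, the lower limit is 0.025^(1/n) and the upper limit is 1

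A check for infectious diarrhea that used the tube result would keep only tube-positive patients. Each of them has a usable sample by construction, so the proportion is 100% whatever the true rate.

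| Assumed usable, all 50 | Proportion (95% CI) | Kept at 10% positive | Kept at 20% positive | Kept at 50% positive |
|---|---|---|---|---|
| 30/50 | 60% (45.2–73.6) | 3/3 | 6/6 | 15/15 |
| 40/50 | 80% (66.3–90.0) | 4/4 | 8/8 | 20/20 |
| 45/50 | 90% (78.2–96.7) | 4/4 | 9/9 | 22/22 |

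Example: 40 × 0.20 = 8 kept, so 8/8 = 100%, with lower limit 0.025^(1/8) = 0.631.

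Another calculation drops only the patients without a result: 40/50 becomes 40/40 (91.2–100), a shift of 100 − 80 = 20 points. The same step gives 40 points from an assumed 60% and 10 points from an assumed 90%. But it keeps every pathogen-negative patient, so it is not a check for infectious diarrhea and does not measure the effect of this sentence.

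**Step 6: size under the plan as written.** Nobody is removed. The denominator stays at 50 and the shift is 0 points for every assumed rate.

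**The case for a change.** The strongest argument for a change is that the wording is mandatory, that it refers to the whole list, and that no section expressly limits the check to items known before insertion. Who counts as a relevant patient, and on what information, belongs in a protocol and should not be left to a statistical analysis plan. The benign reading rests on inference, and two or three sentences with no new data would settle the matter.

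Part of this stands. The list does contain the tube's own result, and the phrase about infectious diarrhea is narrower than the entry criterion. A reader could fairly wish it said suspected.

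The step from there to a biased success rate does not stand. It needs someone to apply the sentence after the result is known, and then to remove patients on the strength of it. The protocol instructs neither, and its recruitment sections point the other way. Nor are failed collections singled out: a pathogen-negative patient is just as unconfirmed as one with no result. Whether every attempted patient stays in the denominator is a matter commonly left to the statistical analysis plan, which is not at hand.

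**Conclusion.** No change to the plan is needed. There is a loosely worded statement of purpose that sits awkwardly beside the inclusion criteria, and an analyst would resolve it sensibly: patients are selected at admission on the inclusion criteria, infectious is read as suspected, and the stool sample's date and result serve outcome and description.

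On that reading the effect on the success proportion is zero and all 50 patients remain. This rests on two points in the text: recruitment precedes any tube result, and no exclusion is attached to the relevance statement. The conclusion would differ only if another document, such as an analysis plan, removed patients after the attempt on the basis of the stool result. Nothing in the protocol calls for that.
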